Cognitive control – “a system that modulates the operation of other cognitive in the service of goal-directed behavior” [9] – is held as a core cognitive deficit in schizophrenia and is considered a construct that could be useful in dimensional investigations that span across psychiatric diagnoses. CC is critically recruited when prepotent modes of responding are not adequate. Accordingly, altered performance in SZ in the Preparing to Overcome Prepotency (POP) task, a cued stimulus-response reversal tasks, is associated with reduced engagement of prefrontal gamma activity. Updating and maintenance of goal-relevant information, such as object location in a spatial working memory (SWM) task, also induces frontal gamma activity. In these tasks gamma power is characteristically modulated by theta phase (theta-gamma coupling). While direct evidence of such coupling alterations in SZ has not been reported, convergent observations from both animal and human studies point to the functional relevance of the phenomenon and motivated the proposal of its involvement as the basis of WM dysfunctions in the disorder (Lisman, 2010). The employment of CC and WM tasks appears therefore to be particularly suited not only to track cognitive changes secondary to tDCS, but also to provide biomarkers that can inform translational models of the disorder and therapy.

Such neuronal synchronization changes can be robustly measured by EEG. MRI makes the challenge to localize their source in two ways: structural scans provide the anatomical information to advanced source localization algorithms and fMRI provide complementary information about DLPFC involvement in task execution. In the framework of the cellular machinery involved in the gamma cycle, excitation-inhibition balance shifts are tied

to the interplay between pyramidal neurons and fast-spiking, parvalbumin positive interneurons, which is neurochemically mediated by glutamate and GABA. MR spectroscopy correlates of tDCS – polarity specific effects on Glx:NAA and GABA:NAA (Stagg 2009) are consistent with involvement of this machinery and support the methodology to further detail DLPFC tDCS effects.

Study Design

This is an interventional study assessing efficacy and neurophysiological correlates of tDCS in schizophrenia patients in a randomized, double-blind parallel-arm design. The expected duration of the study is 2 years.

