The following schematics outline the study design and the stimulation strategy. We will recruit 40 participants and may screen up to 60 people to achieve target subject population. Subject involvement will last approximately 2 months, including a stimulation session block - 2 daily 20 minute sessions over 5 consecutive days - and assessment sessions.

Participants will be pseudo-randomized into an active stimulation or sham stimulation arm, matched for cognitive impairment at baseline. Both acute and maintenance effects are evaluated through clinical and cognitive assessment and neuroimaging sessions at 4 time points baseline, after the first stimulation session, after 1 week and follow-up at 2 months.

Sub Study:

This is an interventional study assessing efficacy and neurophysiological correlates of tDCS in schizophrenia patients in a within subject design. The duration of the study will be in line with the 2 years of the main study. We will recruit a maximum of 20 participants. The participants will be recruited from the sham condition of the main study. After the two month follow-up (in the main study), the participants, who were randomized into the sham condition, will be asked to participate. Participation will be optional. Subject involvement will last an additional 2 months.

Study Population

We will recruit 40 subjects with a diagnosis of schizophrenia, schizopreniform disorder or schizoaffective disorder and taking antipsychotic medication. Medication history will be fully assessed with antipsychotic exposure converted into standardized equivalents.

Inclusion Criteria: a) ages 18-50 years; b) on stable doses of antipsychotic medication for at least one month; c) not taking benzodiazepines or mood stabilizers; d) Mild to severe cognitive impairment in MATRICS Consensus Cognitive Battery (composite scores < 40). Exclusion Criteria: a) DSM-5 mental retardation; b) significant head injury; c) medical illness affecting brain function or structure; d) pregnancy or postpartum (<6 weeks after delivery or miscarriage); e) significant neurologic disorder (e.g seizure disorder); f) inability to provide informed consent; g) significant color blindness that affects task performance; h) comorbidity for DSM-5 psychoactive substance use disorder within the past one month; i) positive urine drug screen (excluding THC at baseline); j) temporal relation between illness onset and head injury; and k) Taking benzodiazepines or mood stabilizers (lithium allowed).

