Sub Study:

We will only recruit from the 20 participants who were randomized into the sham condition of the main study. Inclusion: Completion of the sham condition of the main study. Exclusion: Participation in the active stimulation condition of the main study. Additionally, if the participant has 1) become pregnant, 2) stopped their antipsychotic medication 3) began taking benzodiazepines or mood stabilizers (lithium allowed), or 4) met criteria for DSM-5 psychoactive substance use disorder within the past one month, they will no longer be eligible for the sub-study.

Subject recruitment

Subjects will be recruited from the outpatient clinical programs at Baylor College of Medicine and other community psychiatric programs. These will include Ben Taub's psychiatric emergency room and inpatient and outpatient center and MHMRA. Primary clinicians at BCM will be notified of our research study. Potential subjects with a diagnosis of schizophrenia will be identified and initially approached through their primary clinician, who will ask patient's permission to be contacted by the research team. Upon obtaining patient's written permission, a staff member from the research team will contact the subject. We will also recruit participants through flyers in the community and social media, such as facebook and BCM's clinical trials website.

The screening and recruitment procedure is listed below:

Screening:

- Eligibility checklist
- Ishihara Color Blindness Test
- Urine Pregnancy test for females
- Urine drug screen, if not available from inpatient/outpatient testing

Sub Study:

- Eligibility Checklist
- Urine pregnancy test for females
- Urine drug screen, if not available from recent inpatient/outpatient testing

Screening before experimental procedures:

- EEG and MRI screening protocol prior to participating in imaging studies

Symptoms and Neuropsychological assessment: Interviews and Ratings

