Participants will be interviewed in a dedicated room at the Greenpark One building. One of the following two cognitive batteries may be administered. The BACS battery, a newly developed instrument that assesses cognitive impairments in schizophrenia takes approximately 35 minutes to complete. The constructs that are measured include verbal memory, working memory, motor speed, verbal fluency and executive functioning. The other cognitive assessment tool that could be used is the MATRICS assessment. The full MATRICS battery targets the six cognitive domains (speed of processing; attention/vigilance; working, visual and verbal memory; reasoning and social cognition) identified as being disturbed in schizophrenia. The MATRICS battery takes approximately 1 hour.

Sub Study:

MATRICS will be completed at the 1 week time point.

Safety and tolerability assessment

Clinical and neuropsychological assessments are all performed by trained research personnel to reduce the risk of distress from psychiatric interviews and experimental procedures.

Clinical Assessments

In addition to detailed demographic information (including medication and treatment information), we obtain diagnostic information using the Structured Clinical Interview for DSM-5 Disorders (SCID-5) and/or the MINI International Neuropsychiatric Interview for Psychotic Disorders Studies (MINI 7.0.2) at the discretion of the PI. Psychopathological ratings are conducted include: the Brief Psychiatric Rating Scale (BPRS), the Scale for the Assessment of Positive Symptoms (SAPS), the Scale for the Assessment of Negative Symptoms (SANS), the

Hamilton Depression Rating Scale (HDRS), the Bech-Rafaelsen Manic Rating Scale, the 7-point Clinical Global Impression (CGI) Scale, the Global Assessment Functioning (GAF), Auditory Hallucinations Rating Scale (AHRs), and Specific Level of Functioning Scale (SLOF).

Sub Study:

Psychopathological ratings listed above will be completed at the 1 week time point and 2 month time point.

Medical assessments

A medical history will be obtained on all participants.

Experimental Procedures: tDCS, EEG, MRI

tDCS

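### Allocation is described only as pseudo-randomization matched on a known baseline score, and the sub-study offer reveals each completer's arm, so later allocations could become predictable

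*Combined protocol and SAP*

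**What the plan says.** The Objectives and Study Design sections both describe the trial as randomized; Study Design has it "in a randomized, double-blind parallel-arm design". The one sentence on how arms are assigned, also in Study Design, is: "Participants will be pseudo-randomized into an active stimulation or sham stimulation arm, matched for cognitive impairment at baseline".

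The Sub Study paragraph of Study Design states that, once the two-month follow-up is over, "the participants, who were randomized into the sham condition, will be asked to participate". It places the sub-study within the same two years as the main study. Study Population, Sub Study, adds: "We will only recruit from the 20 participants who were randomized into the sham condition of the main study". It excludes anyone treated in the active arm.

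A MATRICS composite below 40 is an inclusion criterion. On who does the testing, the safety paragraph after the neuropsychological assessments says: "Clinical and neuropsychological assessments are all performed by trained research personnel". On numbers: "We will recruit 40 participants and may screen up to 60 people to achieve target subject population".

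The protocol does not say how the sequence is generated, how matching works for participants who arrive one at a time, which score is used for matching, who holds the code, who is blinded, who makes the sub-study offer, or when an individual's arm may be revealed.

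**The concern.** Three features combine.

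- **Method.** Matching on a baseline score is not in itself random allocation. Under some matching rules, the arm of a later participant is fixed by the arm of an earlier one.
- **A visible matching variable.** Cognition is scored by research personnel to establish eligibility, so the score is known before allocation.
- **Disclosure.** The sub-study offer goes to sham completers only, which reveals both arms.

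If the people who enrol can work out the next arm, they can, even without intent, influence who enters and when. Adjusting for baseline cognition does not remove selection on prognosis that was not measured. It cannot be repaired after enrolment. Raters who learn which completers were in which arm may also come to recognise response patterns in participants still under follow-up.

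**Working it through.** **No figure to reproduce.** The plan gives no power, effect size or allocation algorithm. The one available check is that 20 sham of 40 implies 1:1, since 40 × 0.5 = 20.

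**Inputs from the protocol:** 40 participants; 20 sham; arm revealed about 2 months after entry; 2-year study.

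**Assumptions:** uniform accrual over 16 to 24 months (24 is an outer limit, since follow-up must also fit in the two years); pair matching within K equal bands of baseline cognition; an observer who knows the scheme and every disclosed arm.

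**Exposure.** Enrolled per 2-month lag: 40 × 2/16 = 5 down to 40 × 2/24 = 3.3. Share enrolled after the first arm could be disclosed: 1 − 2/16 = 88% to 1 − 2/24 = 92%.

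**Predictability.** In a pair, the second member's arm is certain only if the first member's arm is already disclosed. Otherwise it is a coin toss. So guessed correctly = certain + (1 − certain)/2. Simulated results over 16 to 24 months' accrual:

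| Bands | Certain, 2-month lag | Guessed, 2-month lag | Certain, arms known at once | Guessed, arms known at once |
|---|---|---|---|---|
| 1 | 0–2% | 50–51% | 50% | 75% |
| 2 | 3–9% | 52–54% | 49% | 74% |
| 4 | 12–19% | 56–60% | 47% | 74% |
| 8–20 | 21–29% | 60–64% | 38–45% | 69–73% |

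Hand check, one band: a gap of 2 months or more between successive entries has probability (1 − 2/A)^40, where A is the accrual period in months, and half of the entries are second members. For A = 20: 0.9^40 / 2 = 0.0148 / 2 = 0.7%. For A = 24: 0.0308 / 2 = 1.5%. Both agree with the first row.

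If arms are never disclosed to those who enrol, the result is 0% certain and 50% guessed under every scheme simulated. If disclosure at 2 months stays and pairs are replaced by blocks of 4 in two bands, 4–8% are certain and 54–57% guessed. Changing the block size alone therefore gains nothing.

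**Bias.** Let d be the difference in mean prognosis between arms among the certain allocations, in SD. Then the shift in the treatment contrast is d × share certain. With d = 0.3 (assumed):

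- one band: at most 0.3 × 0.02 = 0.006 SD
- two bands: 0.3 × 0.03 = 0.009 to 0.3 × 0.09 = 0.027 SD
- fine matching: 0.3 × 0.21 = 0.063 to 0.3 × 0.29 = 0.087 SD
- upper bound, arms known at once: 0.3 × 0.50 = 0.15 SD

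The shift is proportional to d. From two bands to the finest matching it runs 0.003–0.029 SD at d = 0.1 and 0.015–0.145 SD at d = 0.5.

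For scale, 20 per arm detects 0.91 SD at 80% power (two-sided 5% t-test, also an assumption). So 0.087/0.91 is about 10%, and 0.15/0.91 about 16%.

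**The case against.** The allocation sentence is compatible with sound practice. Pseudo-randomization may simply mean constrained randomization. Stratification, group-level balancing, or minimisation with a random element, run by someone independent, would all fit the wording and be close to unpredictable. The sub-study text also speaks of participants having been randomized. This objection stands, and it is why predictability is stated as a possibility.

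A reader might infer more in four places, and the documents do not support it.

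- **That half of the allocations are determined and about 74% can be guessed.** This needs pair matching and every earlier arm known at once. Disclosure through the sub-study comes two months after entry.
- **That disclosure is stated to be rolling.** It is not. It is the natural reading, because the offer follows the two-month visit, the sub-study shares the two-year window and its cognitive and EEG schedule starts on the first day of stimulation. But if accrual ended by about month 20, offers held until the last follow-up at month 22 could still fit, with the sub-study ending at month 24.
- **That one small team recruits, tests, stimulates and rates.** The protocol refers only to research staff. It gives neither their number nor their overlap.
- **That the offer unblinds the participant's own main-study results.** Each person concerned has already finished main-study follow-up. The exposure is to later entrants and to ratings still to be made.

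**Conclusion.** The concern holds as a risk that the protocol leaves open. The design label and the stated allocation method do not match, the likely matching score is known before allocation, and the sub-study offer reveals completers' arms with no safeguard stated. This goes beyond missing detail, because following the text as written can expose later allocations.

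The size ranges from negligible with one or two bands (0–9% of allocations certain) to material with fine matching (21–29% certain), with a shift from under 0.01 to about 0.09 SD at 0.3 SD of steering. The 0.15 SD figure is an upper bound that requires immediate knowledge of arms, which no section describes. The accrual period, pair matching, number of bands and degree of steering are all assumptions. The protocol does not let a reader tell which end of the range applies.

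**What to change.** Replace the allocation sentence in Study Design with:

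- 1:1 randomization from a computer-generated list, stratified by the baseline MATRICS composite (for example two strata) with varying block sizes;
- the list held by an existing team member with no role in enrolment or rating, or pre-loaded as stimulator codes;
- each assignment released only after eligibility is confirmed.

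State who is blinded, and add the MATRICS composite as a covariate in the Data Analysis model, which at present names none.

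In the Sub Study text, state that individual assignments are withheld from enrolling and rating staff until the last main-study follow-up. There are two ways to do this: the code holder makes the offer and those staff stay out of sub-study sessions, or all offers wait until main-study follow-up ends. Most of the gain comes from this step and from concealment, not from the block sizes.

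The cost is protocol wording and a list generated once, with no extra participants. Balance on cognition is slightly less exact than with matching, and the covariate largely recovers this. The first option requires some separation of roles. The second delays the sub-study and fits the two years only if accrual ends by about month 20 (20 + 2 + 2 = 24). If a concealed scheme with a random element is already in use, describing it and adding the withholding rule is enough.

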tDCS intervention consists of two daily sessions, separated by 1 hour, over 5 consecutive days. Such strategy is commonly used in clinical studies, yielding prolonged clinical effects while being well-tolerated. Electrical stimulation will be delivered by a constant-current multi-channel stimulator (NeuroMod tXES Stimulator, RGN, New Mexico, USA) through conductive-rubber electrodes placed in sponges saturated with saline (0.9% NaCl). As per schematic in the figure inlay, left DLPFC will be targeted positioning the anode electrode midway between F3 and FP1 location of the 10-20 system. The cathode electrode will be positioned over left TPJ, midway between T3 and P3.

Patients in the treatment group will receive 20 min of 2 mA direct current stimulation with 20 sec fade in/out. The Sham group will undergo exactly the same procedures but stimulation (aside from the initial and last 20 seconds) will consist of brief (1 sec) low current (.11 mA) pulses every 10 sec.

Sub Study:

All subjects in the sub study will receive the active treatment consisting of 20 min of 2 mA direct current stimulation with 20 sec fade in and fade out.

Safety and tolerability assessment

The stimulation strategy and the electrode montage used in the present studies are commonly reported as well tolerated.

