The risks to subjects related to receiving tDCS are minimal and confined to discomfort, such as itching and tingling on the scalp (Brunoni et al. 2011). However in rare instances, some participants may experience the stimulation as a stinging sensation that is uncomfortable. Very rarely, there may be heating and even burning of skin. Skin lesions do not occur with modern microchip controlled stimulators, accordingly the NeuroMod tXES stimulator meets the highest safety standards by micro-processor-controlled current outflow with multistage monitoring of the impedance. As discomforting sensations are more often reported when current is abruptly started or stopped, active current levels will be achieved by slowly ramping up current from zero and the stimulation will be interrupted through fading it out. Periodically subjects will be actively required to provide a feedback about their degree of comfort and they will be able to speak with experimenters at all time. Subjects will also be asked to rate their pain from 0 to 10 (11 point scale) using a numerical rating scale (NRS) for a standardized assessment of pain. Literature suggests compliance at high tolerability for the used current levels. In the rare event of subject reporting the stimulation highly discomforting or intolerable, the stimulation will be promptly stopped. If the subject is unwilling to resume the protocol, he/she will be drop out from the study. In addition, we will collect a tDCS adverse event screening questionnaire. The questionnaire will be administered after the first session of tDCS and again at the last tDCS session. Participants will have the option to apply topical lidocaine on the scalp 20 minutes prior to tDCS in order to minimize the chance of uncomfortable stimulation. This will likely reduce the possibility of participants dropping out of the study who may be more sensitive to the stimulation.

Cognitive testing and EEG

Cognitive effects will be evaluated the day prior and one week after the first tDCS session to assess acute effects compared to baseline, and two months later to evaluate their persistence. Immediate effects after the first tDCS application will also be investigated in order to explore early response predictors.

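### A participant who stops intolerable stimulation appears to leave the study, and no later assessments, analysis set or partial-data method are planned; a low-priority gap that is cheap to close

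*Combined protocol and SAP*

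**What the plan says.** The relevant text is in five places in the combined protocol and SAP.

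- **tDCS, Safety and tolerability assessment.** "In the rare event of subject reporting the stimulation highly discomforting or intolerable, the stimulation will be promptly stopped". The next sentence is: "If the subject is unwilling to resume the protocol, he/she will be drop out from the study". The same paragraph offers optional topical lidocaine and comments: "This will likely reduce the possibility of participants dropping out of the study who may be more sensitive to the stimulation". No stop rate is given.
- **tDCS (the two arms).** Active: "Patients in the treatment group will receive 20 min of 2 mA direct current stimulation with 20 sec fade in/out". For sham, the procedures are the same but "stimulation (aside from the initial and last 20 seconds) will consist of brief (1 sec) low current (.11 mA) pulses every 10 sec".
- **Study Design.** Assessments include "neuroimaging sessions at 4 time points baseline, after the first stimulation session, after 1 week and follow-up at 2 months". The target is 40 participants. Study Population, Sub Study gives the sham arm size: "We will only recruit from the 20 participants who were randomized into the sham condition of the main study".
- **Data Analysis.** Outcomes go into a GLM for the group-by-time interaction with planned contrasts. The section expects very little missing data, of the missing-at-random kind. Its reasons are published studies, the team's experience, the short duration and the similarity of the two arms' conditions. It states no analysis set and no treatment of incomplete cases.
- **Informed Consent.** Participants may withdraw consent at any time.

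**The concern.** Stopping the intervention and stopping follow-up are different events. Because the drop-out sentence directly follows the one on halting stimulation, it reads as turning the first into the second. The lidocaine remark points the same way, since it links sensitivity to stimulation with leaving the study. A participant who leaves in the treatment week then has no 1-week or 2-month outcome, and those visits carry the main comparison and the test of persistence.

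The trigger is discomfort from the assigned stimulation, which differs between arms apart from the first and last 20 seconds. Losses could therefore be uneven. If they are, and if leavers would have changed differently from those who stay, the group-by-time contrast no longer compares the groups as randomised. The bias could go in either direction. Each loss is 1/20 = 5% of an arm.

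Pain ratings, the adverse-event questionnaire and the DSMB may reveal uneven intolerance, but they neither recover uncollected outcomes nor supply an analysis method.

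**Working it through.** The plan gives no dropout rate, alpha, effect size or SD, so it has no figure to reproduce. What follows is an illustration.

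**Inputs from the documents.** 40 participants in total and 20 in sham, hence 40 - 20 = 20 active.

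**Assumptions.** No true effect; two-sided 5% t-test on change; completers only; leavers' mean change g = 0.5 or 1.0 SD below their arm mean; loss counts and stop rates chosen for illustration.

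**Step 1: bias for given losses.** If d of 20 leave and their mean change is g below the arm mean, the mean of those retained rises by d·g/(20 - d). With d_a active and d_s sham losses:

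bias = d_a·g/(20 - d_a) - d_s·g/(20 - d_s)

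The false-positive rate comes from the noncentral t with n_a + n_s - 2 degrees of freedom and noncentrality bias/√(1/n_a + 1/n_s), where n_a = 20 - d_a and n_s = 20 - d_s.

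| Lost, active/sham | Bias, g = 0.5 | Bias, g = 1.0 | False-positive rate |
|---|---|---|---|
| 1/0 | 0.5/19 = 0.026 | 1/19 = 0.053 | 5.1-5.3% |
| 3/1 | 1.5/17 - 0.5/19 = 0.062 | 3/17 - 1/19 = 0.124 | 5.4-6.5% |
| 4/0 | 2/16 = 0.125 | 4/16 = 0.250 | 6.5-11.2% |
| 2/2 | 0 | 0 | 5.0% |

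The signs reverse if leavers would have done better. If the 1.0 SD gap is measured against those retained instead of the arm mean, the 4/0 case is 4 × 1/20 = 0.20 SD and 8.9%.

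**Step 2: how likely such losses are.** Take active losses as Binomial(20, p), with no sham losses (the least favourable split), and average the step 1 rate over the number lost.

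| Assumed stop rate p | Expected losses, 20p | P(3 or more) | P(4 or more) | Average false-positive rate, g = 0.5 to 1.0 |
|---|---|---|---|---|
| 2% | 0.4 | 0.7% | 0.06% | 5.0-5.2% |
| 5% | 1 | 7.5% | 1.6% | 5.2-5.7% |
| 10% | 2 | 32% | 13% | 5.5-7.2% |

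Worked example, p = 2% and g = 1.0. The step 1 formula gives 6.28% for 2/0 and 8.16% for 3/0. The average is 0.668 × 5.00 + 0.272 × 5.29 + 0.053 × 6.28 + 0.0065 × 8.16 + 0.0006 × 11.2 ≈ 5.2%.

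**Step 3: what continued follow-up recovers.** In the 4/0 case with g = 1.0, if two of the four leavers attend, two remain missing from 18 observed. Bias is 2 × 1/18 = 0.11 SD instead of 0.25 SD, and the false-positive rate is 6.3% instead of 11.2%. If all four attend, the bias is zero.

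**The case against.** The other side has four arguments.

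1. **Wording.** The sentence speaks of resuming the protocol, not the stimulation. Someone who refuses the whole protocol is withdrawing, which Informed Consent always allows. This reading is possible. It removes the complaint about the rule, but leaves the absence of an analysis set and a partial-data method.
2. **The plan's own expectation.** Data Analysis gives reasons for expecting little missing data, and the similarity of the arms is a direct argument against uneven loss. It has some force: the first and last 20 seconds are exempt from the sham reduction, and the safety text says "As discomforting sensations are more often reported when current is abruptly started or stopped". But it remains an expectation. It does not say what is done with the data that do go missing, and similarity is weakest between the ramps, where the currents differ.
3. **Uneven loss is conjecture.** A reader might infer that tolerability dropout will be higher in the active arm and will bias the result. The documents do not support this. They call the event rare, cite good tolerability at these current levels, use slow ramping, offer lidocaine and give no rate in either arm. This objection stands in full.
4. **Completers only is not the stated analysis.** A reader might also infer that leavers will be excluded. The plan does not say so. Leavers would have a baseline assessment, and possibly the one after the first session. The figures therefore illustrate one analysis the text allows, not the one planned. This also stands.

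**Conclusion.** The gap is real and its likely effect is small. The plan does not say that participants who stop stimulation and still consent will be assessed at 1 week and 2 months, and it names neither an analysis set nor a method for partial data. That holds on either reading of the drop-out sentence.

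If intolerance is as rare as the protocol says, the average false-positive rate stays close to 5%. It becomes noticeable only near a 10% stop rate, which is hard to reconcile with a rare event. The 4/0 case (0.13-0.25 SD, 6.5-11.2%) is an unlikely upper bound and should not be quoted as the expected bias. There is no bias if losses are equal and alike in the two arms, or if leavers would have changed as much as those who stayed.

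All sizes rest on assumed loss counts, stop rates and gaps, and on a completers-only analysis. This is a cheap improvement of low priority, not a serious flaw.

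**What to change.** Leave the rule for interrupting stimulation as it is, and add the following.

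- **Follow-up.** State that participants who stop stimulation and still consent are invited to their remaining scheduled 1-week and 2-month assessments.
- **Analysis.** State that all randomised participants are analysed in their assigned arm, with a likelihood-based mixed model using all available visits.
- **Reporting.** Report stopping of stimulation and dropout from the study, with reasons, by arm.
- **Optional.** Add one simple sensitivity analysis for data not missing at random. An elaborate set of scenarios is not needed in a study of 40.

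The cost is protocol and consent wording, plus a few visits already on the schedule. The estimate will include partially treated participants and may be somewhat smaller. Outcomes after full withdrawal of consent stay missing, so bias is reduced but not always removed. The follow-up statement has to be in place before participants leave, because outcomes not collected then cannot be recovered.
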